4.2. Sub-Study Exclusion Criteria

Subjects presenting with any of the following characteristics/conditions will not be included in the study:

1. Subjects who are receiving other concomitant non-biologic csDMARDs, eg, leflunomide, sulfasalazine.
2. Subjects receiving MTX by a route other than oral.
3. Subjects receiving MTX at a dose lower than 7.5 mg per week or >20 mg per week.
4. Subjects who are investigational site staff members directly involved in the conduct of the trial and their family members, site staff members otherwise supervised by the investigator, or subjects who are Pfizer employees directly involved in the conduct of the trial.
5. Subjects that have become pregnant during study A3921092 and breastfeeding females and females of child-bearing potential who are unwilling or unable to use a highly effective method(s) of contraception as outlined in this protocol for the duration of the study and for at least one ovulatory cycle after last dose of investigational product or females planning pregnancy.
6. Women of childbearing potential must test negative for pregnancy prior to enrollment in this study. (Further description of the requirements and a list of contraceptives considered highly effective and acceptable for use in this study will be found in [Section 4.4.6](#)).
7. Current or recent history of uncontrolled renal, hepatic, hematological, gastrointestinal, metabolic (including hypercholesterolemia), endocrine, pulmonary, cardiovascular, or neurologic disease.
8. Subjects who have been diagnosed with any autoimmune rheumatic disease other than PsA (including systemic lupus erythematosus, mixed connective tissue disease, scleroderma, polymyositis) or diagnosis of fibromyalgia, without approval by Sponsor. Also excluded are subjects with prior history of, or current, rheumatic

- inflammatory disease other than PsA (eg, gout, reactive arthritis, chronic Lyme disease) without approval by Sponsor.
9. A subject who has been diagnosed with immunodeficiency disorder during study A3921092.
 10. Functional Class IV status as defined by the American College of Rheumatology classification of functional status for RA, ie, limited in ability to perform usual self-care, vocational and avocational activities.¹⁵
 11. History of an infected joint prosthesis at any time, with the prosthesis still in situ.
 12. History of any lymphoproliferative disorder, such as Epstein Barr Virus (EBV) related lymphoproliferative disorder, history of lymphoma, leukemia, or signs and symptoms suggestive of current lymphatic disease.
 13. History of recurrent (more than one episode) herpes zoster or disseminated (a single episode) herpes zoster or disseminated (a single episode) herpes simplex.
 14. History of active infection (including localized infection):
 - Requiring hospitalization, parenteral antimicrobial therapy, or as otherwise judged clinically significant by the investigator, within the 3 months prior to sub-study entry;
 - Requiring oral antimicrobial therapy within 2 weeks prior to enrolling in the sub-study.
 15. Any subject who has been vaccinated with live or attenuated vaccines within the 6 weeks prior to the first dose of sub-study medication or is to be vaccinated with these vaccines at any time during treatment or within 6 weeks following discontinuation of study medication. (See [Section 4.4.2 Vaccine Guidelines](#) of LTE study for further information regarding avoidance of household contacts who may be vaccinated).
 16. A subject with any condition possibly affecting oral drug absorption, eg, gastrectomy, clinically significant diabetic gastroenteropathy, or certain types of bariatric surgery such as gastric bypass. Procedures such as gastric banding, that simply divide the stomach into separate chambers, are NOT exclusionary.
 17. A subject who is considered at increased risk for GI perforation (eg, patients with diverticulitis) by the Investigator or Sponsor.
 18. A subject with a malignancy or with a history of malignancy, with the exception of adequately treated or excised non-metastatic basal cell or squamous cell cancer of the skin or cervical carcinoma in situ.

19. A subject requiring prohibited concomitant medications (See [Appendix 3](#)). For a medical condition in which it is important for the subject's safety to continue a prohibited drug described in [Appendix 3](#), and there is no study-permitted alternative, the subject must not participate in this study. Subjects receiving non-prohibited concomitant medications must be on a stable regimen which is defined as not starting a new drug or changing dosage within seven days or 5 half-lives (whichever is longer) prior to the baseline visit.
20. A subject known to be infected with human immunodeficiency virus (HIV), hepatitis B virus or hepatitis C virus or any chronic infection.
21. A subject with evidence of skin conditions (eg, eczema) at the time of the screening or baseline visit that would interfere with evaluation of psoriasis.
22. Other severe acute or chronic medical or psychiatric condition or laboratory abnormality that may increase the risk associated with study participation or investigational product administration or may interfere with the interpretation of study results and, in judgement of investigator, would make subject inappropriate for entry into this study.
23. A subject who, in the opinion of the investigator or Pfizer (or designee), will be uncooperative or unable to comply with study procedures.
24. Participation in other studies involving investigational drug(s) (Phases 1-4) during sub-study participation.

4.3. Sub-Study Enrollment Criteria

Subjects will be enrolled into the sub-study provided they have signed an informed consent document to participate in the sub-study, have undergone all Sub-study Switch /Baseline visit procedures as required, and have met all inclusion and exclusion criteria for participation in the sub-study at the Combined A3921092 Sub-study Switch/Baseline visit. Subjects will be assigned a new subject identification number that will be retained throughout the sub-study.

4.4. Life Style Guidelines

In order to participate in the study, subjects must be made aware of the following life style guidelines and restrictions that apply during and after the study period. Details of these life style guidelines are provided in the sections as noted.

- On designated study visit days, comply with fasting requirements for at least 9 hours prior to visit (See Sub-Study [Section 6](#)).
- On study visit days, do not smoke or ingest caffeine (eg, tea, coffee, some soft drinks/colas/energy drinks and power bars) during the 30 minutes prior to blood pressure and pulse (heart) rate measurements.

- On study visit days, showering or bathing is permitted prior to attending the study visit, but do not moisturize.
- Avoid vaccinations with live or attenuated live vaccines and contact with individuals who have recently received live or attenuated live vaccines (See [Section 4.4.2](#) of main LTE study).
- Discontinue and avoid using certain medications and treatments used to treat PsA or psoriasis (see [Inclusion Criteria](#) and list of prohibited medications [Appendix 3](#)). Discontinue and avoid using certain other prohibited medications and treatment (see [Appendix 3](#)) not used to treat PsA or psoriasis. For a medical condition in which it is important for the subject's safety to continue using the prohibited drug, and there is no study-permitted alternative, the subject must not participate in this study.
- Contact the study site investigator if there are any changes or additions to concomitant medications.
- Avoid having elective surgery (See [Section 4.4.5](#)).
- Agree to use highly effective contraceptive methods per [Section 4.4.6](#).

4.4.1. Non-Pharmacologic Interventions

The subject should continue all non-pharmacological therapies, such as physical therapy, as indicated.

4.4.2. Vaccine Guidelines

For guidance on administration of vaccines to a subject and management of household contacts with others vaccinated refer to [Section 4.4.2](#) of the main study A3921092.

4.4.3. Dietary Supplements

For the purposes of this protocol, dietary supplements are defined as vitamins, minerals, purified food substances, and herbals with pharmaceutical properties.

Vitamins, minerals and purified food substances are allowed in amounts not known to be associated with adverse effects (such as hypervitaminosis). Herbals with pharmaceutical properties are allowed only if there is acceptable evidence of no CYP3A inhibition or induction. Otherwise, herbals with pharmaceutical properties must be discontinued for at least 4 weeks prior to first dose of study drug, unless there is sufficient data available regarding the duration of an herbal medication's pharmacokinetic and pharmacodynamic effects to allow a shorter washout to be specified (eg, 5 half-lives). Please direct any questions to the Sponsor.

Glucosamine sulfate and chondroitin sulfate are allowed in the study but should be stably dosed beginning at least 1 week prior to first dose of study medicine.

4.4.4. Fasting Visit Requirements

On visit days when fasting lipid panels are scheduled to be collected, all subjects should refrain from all food and liquids (water and medications permitted, if appropriate) for at least 9 hours prior to scheduled safety laboratory tests. Visits that require fasting are Baseline, Month 6 and Month 12, End of Treatment/Early Termination Visit and Follow-Up Visit (if required).

4.4.5. Elective Surgery

During the course of this trial, no elective surgery should be scheduled without first consulting the Pfizer Study Clinician.

Subjects who do require surgery should temporarily discontinue study drug for one week prior to the surgical procedure and remain off study drug after the surgical procedure until sutures/staples are removed. If absorbing sutures or chemical closure methods are utilized, study drug can be resumed when the operative site is sufficiently healed and risk of infection is minimal.

4.4.6. Contraception

4.4.6.1. Contraceptive Methods in Women of Childbearing Potential

Administration of tofacitinib in preclinical studies was shown to have teratogenic effects on the offspring of treated rats and viability of their fetuses. Due to this hypothetical risk, women of childbearing potential will not be administered tofacitinib until pregnancy is excluded and should use a highly effective method(s) of contraception during therapy with tofacitinib and for at least one ovulatory cycle after study treatment is discontinued. They must have a negative urine pregnancy test at the baseline visit prior to the first dose of study drug and at every visit during the study (or more frequently if required by local practices), if a menstrual cycle is missed, or if potential pregnancy is otherwise suspected or if the subject has become sexually active.

In this study, male subjects who are able to father children and female subjects who are of childbearing potential will receive MTX or placebo in a blinded manner. MTX has been associated with teratogenic risk. For subjects who are sexually active and at risk for pregnancy with their partner(s) must agree to use with their partner(s) two (2) methods of highly effective contraception throughout the study and continue for at least 3 months after the last dose of sub-study drug.

For the purposes of this protocol, female subjects must either use adequate contraception or be of non-childbearing potential. The investigator, in consultation with the subject, will select an appropriate method(s) of contraception for women of child-bearing potential who are sexually active from the permitted list of contraception methods, and instruct the subject in their consistent and correct use. The investigator, at each study visit, will confirm and document consistent and correct use. In addition, the investigator will instruct the subject to call immediately if a selected birth control method(s) is discontinued or if pregnancy is

known or suspected. Subjects in the United Kingdom that are women of childbearing potential are required to use two highly effective methods of birth control.

Highly effective methods of contraception are those that, alone or in combination, result in a failure rate of less than 1% per year when used consistently and correctly (ie, perfect use) and include:

1. Established use of oral, injected, injected or implanted hormonal methods of contraception are allowed provided the subject remains on the same treatment throughout the entire study and has been using that hormonal contraceptive for an adequate period of time to ensure effectiveness.
2. Correctly placed copper containing intrauterine device (IUD) or intrauterine system (IUS).
3. Male condom or female condom used WITH a spermicide (ie, foam, gel, film, cream, suppository). For countries where spermicide is not available or condom plus spermicide is not accepted as highly effective contraception, this option is not appropriate.
4. Sterilization of male partner with appropriately confirmed absence of sperm in the post-vasectomy ejaculate.
5. Bilateral tubal ligation or bilateral salpingectomy or bilateral tubal occlusive procedure (provided that occlusion has been confirmed in accordance with the device's label).

NOTE: Sexual abstinence, defined as completely and persistently refraining from all heterosexual intercourse (including during the entire period of risk associated with the study treatments) may obviate the need for contraception ONLY if this is the preferred and usual lifestyle of the subject.

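### Sub-study exclusion criterion 5 keeps the main study's one-cycle contraception period, although Appendix 10 Section 4.4.6.1 requires two methods for at least 3 months because of methotrexate

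*Protocol*

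**What the plan says.** All references are to Protocol Appendix 10 unless stated.

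- **Section 4.2, exclusion criterion 5.** It excludes "Subjects that have become pregnant during study A3921092 and breastfeeding females", and also females of childbearing potential who are "unwilling or unable to use a highly effective method(s) of contraception as outlined in this protocol" during the study and "for at least one ovulatory cycle after last dose of investigational product or females planning pregnancy".
- **Section 4.2, criterion 6.** It asks for a negative pregnancy test and refers the reader to Section 4.4.6: "Further description of the requirements and a list of contraceptives considered highly effective".
- **Section 4.4.6.1, first paragraph.** Women of childbearing potential should use highly effective contraception "during therapy with tofacitinib and for at least one ovulatory cycle after study treatment is discontinued".
- **Section 4.4.6.1, second paragraph.** Men able to father children and women of childbearing potential will receive methotrexate or placebo blinded, and methotrexate is described as having a teratogenic association. Those who are sexually active and at risk of pregnancy "must agree to use with their partner(s) two (2) methods of highly effective contraception throughout the study" and must "continue for at least 3 months after the last dose of sub-study drug".
- **Section 4.4.6.3.** Male subjects must take precautions because methotrexate is given.
- **Section 5.** Both tofacitinib and methotrexate are investigational products in the sub-study.

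In the main protocol, exclusion criterion 3 (Section 4.2.1) has the same duration wording as sub-study criterion 5, and main Section 4.4.6.1 also asks for one cycle.

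**The concern.** In the main study, the eligibility criterion and the contraception section agree on one cycle. In the sub-study, the contraception section gained a methotrexate rule, but the numbered criterion kept the old period. The text used to decide who may enter is therefore weaker than the protocol's own safety rule, in both duration and number of methods.

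The agreement obtained at entry matters because the sub-study schedule has no visit 3 months after the last dose. Scheduled visits end at Month 12. The 28-day follow-up visit is required only after discontinuation for laboratory abnormalities or an adverse event, or for clinically significant laboratory findings at the final assessment. What the subject accepts at the start is thus the main safeguard for the later part of the 3 months.

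**Working it through.** The documents give no statistical figure to reproduce. The check sets the texts side by side and then measures the difference between the two periods.

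**Which drug does criterion 5 cover?** Its period runs from the last dose of investigational product. Section 5 counts methotrexate as one, so the one-cycle period cannot be read as applying to tofacitinib only.

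**Number of methods.** Criterion 5 leaves it open (method(s)). The second paragraph of Section 4.4.6.1 says two.

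**Duration.** Criterion 5 gives at least one cycle; Section 4.4.6.1 gives at least 3 months. Both are minimum periods, so a subject who meets the second also meets the first. The reverse is not true: a woman who accepts one method or one cycle, but not two methods for 3 months, meets the literal period in criterion 5 and fails Section 4.4.6.1.

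**Men.** Sections 4.4.6.1 and 4.4.6.3 bind them, but no sub-study exclusion criterion states a contraception requirement for them.

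**Size of the difference.** Difference = 3 months minus one cycle. Inputs:
- 3 months: 3 × 28 = 84 days, borrowing the 28-day visit month of Section 6.2, up to about 91 calendar days.
- One cycle: 28 days, range 21 to 35 days. This is an assumption; the documents give no cycle length.

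Results:
- At a 28-day cycle: 84 − 28 = 56 days (8 weeks) to 91 − 28 = 63 days (9 weeks).
- Smallest: 84 − 35 = 49 days (7 weeks).
- Largest: 91 − 21 = 70 days (10 weeks).

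**Who is covered.** Because methotrexate is blinded, the 3-month rule applies in both arms, planned at about 180 subjects in total (Section 3). It binds only those sexually active and at risk of pregnancy, whose number the documents do not give. Criterion 5's contraception clause concerns only females of childbearing potential, whose number is also not given.

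**The case against.** The strongest defence is that the texts can be read together. Both periods are minimums. Criterion 5 refers to contraception as set out in the protocol, and criterion 6 points to Section 4.4.6. Section 4.4 says that, to participate, "subjects must be made aware of the following life style guidelines and restrictions", and its list includes agreeing to the methods in Section 4.4.6. The one-cycle sentence in Section 4.4.6.1 is framed by tofacitinib, and the methotrexate paragraph is the specific rule. Inclusion criterion 5 requires local contraceptive standards for background DMARDs throughout. Inclusion criterion 2 and exclusion criterion 23 screen out subjects unwilling or unable to comply.

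Much of this stands, and it makes the practical effect small. It does not remove the inconsistency, for three reasons:

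- Criterion 5 states its own duration, so a reader has little reason to look elsewhere for one.
- A reader who follows the pointer first meets a sentence giving one cycle after study treatment. A later sentence requires two methods of women in the United Kingdom, which may suggest that one is enough elsewhere.
- Neither general compliance criterion mentions contraception.

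A reader might infer that the protocol contradicts itself so that both rules cannot be followed. The documents do not support that, since 3 months satisfies both. A reader might also infer that men have no contraception requirement. They do; it is only missing from the numbered exclusion criteria.

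**Conclusion.** The point holds as a minor internal inconsistency in a safety eligibility criterion. Criterion 5 states a shorter period than Section 4.4.6.1 and does not specify two methods, although methotrexate is one of the products it covers. The wording difference is certain from the text. That it came from an incomplete update of the main-study wording is likely but not stated.

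The difference of 49 to 70 days rests on the assumed cycle length and on the two readings of 3 months. It would be tempting to read it as weeks of unprotected exposure to a teratogen, or to apply it to all 180 or so subjects. The documents support neither: Section 4.4.6.1 already protects subjects at a site that follows it, and the affected number is unknown. Nothing here bears on sample size, endpoints or analysis.

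**What to change.** In Appendix 10:

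1. **Criterion 5.** Keep the exclusions for subjects who became pregnant during A3921092, for breastfeeding females and for females planning pregnancy. Keep the contraception clause applying to all females of childbearing potential. Change its post-treatment period to at least 3 months after the last dose of sub-study drug. Add that those sexually active and at risk of pregnancy must be willing and able to use two highly effective methods as in Section 4.4.6.1, with abstinence accepted only under the note in that section.
2. **Men.** Add a matching criterion for men able to father children, in line with Sections 4.4.6.1 and 4.4.6.3.
3. **Section 4.4.6.1, first paragraph.** State that the one-cycle period concerns tofacitinib alone and that the 3-month methotrexate rule governs in the sub-study.

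The condition on sexual activity should attach only to the two-method requirement. Attached to the whole clause, it would release women of childbearing potential who are not currently sexually active and whom criterion 5 now covers. The United Kingdom sentence can stay.

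The cost is a wording clarification: one criterion revised, one added and one sentence in Section 4.4.6.1. Design, visits and analysis are unchanged. The two-method, 3-month rule is already in Section 4.4.6.1; the longer period is new only for females of childbearing potential outside that rule.

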4.4.6.2. Women of Non-Childbearing Potential

Female subjects of non-childbearing potential must meet **at least one of the following criteria:**

- Have undergone documented hysterectomy or bilateral oophorectomy;
- Have medically confirmed ovarian failure; or
- Achieved post-menopausal status defined as: cessation of regular menses for at least 12 consecutive months with no alternative pathological or physiological cause; status may be confirmed by having serum FSH level within the laboratory's reference range for post-menopausal females.

All other female subjects (including females with tubal ligations) will be considered to be of childbearing potential.

4.4.6.3. Contraceptive Methods in Male Subjects

Administration of tofacitinib in preclinical trials demonstrated no effects on male sperm or offspring in any studies conducted to date. Due to the concomitant administration of MTX in this study, male subjects need to take contraceptive precautions as described in the previous section.

4.5. Sponsor Qualified Medical Personnel

Please refer to [Section 4.5](#) of the main Study Protocol A3921092.

5. SUB-STUDY STUDY TREATMENTS

For the purposes of this study, and per International Conference on Harmonisation (ICH) guidelines, investigational product is defined as a pharmaceutical form of an active ingredient or placebo being tested or used as a reference/comparator in a clinical trial, including a product with a marketing authorization when used or assembled (formulated or packaged) in a way different from the approved form, or when used for an unapproved indication, or when used to gain further information about an approved use (ICH E6 1.33). For this sub-study, the investigational products are tofacitinib and methotrexate.

5.1. Sub-Study Allocation to Treatment

The following medication will be supplied by Pfizer Inc:

- Tofacitinib 5 mg tablets (open-label).
- Methotrexate 2.5 mg capsules.
- Placebo capsules that match Methotrexate capsules.

Both the open-label tofacitinib 5 mg and blinded MTX will be dispensed to subjects to self-administer after appropriate training and specific written instructions are provided. Tofacitinib will be taken orally 5 mg BID (approximately every 12 hours). Methotrexate or MTX placebo will be taken orally once a week. The dose of MTX must be the same oral dose as taken prior to sub-study entry; allowed doses of MTX entry may range from 7.5 mg to a maximum of 20 mg a week but must be stable 4 weeks prior to entering the sub-study, and must not be changed with the following exception. Reductions in the dose of MTX are permitted if there is evidence of toxicity. For subjects who are on a MTX dose higher than 7.5 mg per week, the MTX dose may be reduced to 7.5 mg per week on one occasion and with Sponsor's approval. Dose re-adjustments of MTX will be allowed with Sponsor's approval. Reductions of tofacitinib dose are not permitted. Temporary withdrawals of any of the sub-study drugs (tofacitinib and methotrexate/placebo) are only permitted if required

due to safety concerns. Study treatment will continue until the subject discontinues from the study or has received approximately 12 months of treatment.

Allocation of subjects to treatment will proceed through the use of an interactive response technology (IRT) system (interactive Web-based response (IWR)). During the sub-study Baseline visit, the site personnel (study coordinator or specified designee) will be required to enter or select information including but not limited to the user's identification (ID) and password, the protocol number, and the subject's number. The site personnel will then be provided with a randomization number and container number(s) when investigational product is being supplied via the IRT system. The confirmation report must be stored in the site's files.

